4.1.2.1.1 Management of mood alteration

Patient self-rating mood questionnaires GAD-7 (anxiety) (see Table 11) and PHQ-9 (depression) (see Table 12) will be used:

- ◆◆ to support assessment of eligibility at Screening
- ◆◆ to monitor for newly occurring or worsening mood alterations during the study. The following grading system will be used for this study:

At Screening, a patient as judged by the investigator or who meets the cut-off score of ≥ 12 in the PHQ-9 or a cut-off of ≥ 15 in the GAD-7 mood scale, respectively, or select a positive response of '1, 2, or 3' to question number 9 regarding suicidal thoughts or ideation will be excluded from the study.

During the study, patients who meet the cut-off score of ≥ 10 (\geq CTCAE Grade 2 mood alteration) in either questionnaire or indicate a positive response by selecting '1, 2, or 3' to question number 9 on the PHQ-9 must see a psychiatrist for advice on the most appropriate medical treatment must see a psychiatrist for diagnosis and determination of most appropriate medical treatment. For anxiety, this applies only if status has worsened from baseline. Patients who experience \geq Grade 2 mood alteration will be followed by patient self-rating mood scale and will be seen weekly by the psychiatrist until resolved \leq Grade 1 or baseline (for anxiety), if there is no concurrent medical condition that accounts for an acute increase the PHQ score. Questionnaire responses will be checked by the psychiatrist at the weekly visits (until resolution to Grade 1 or baseline (for anxiety).

Table 11. GAD-7 anxiety scale

Over the last 2 weeks, how often have you been bothered by the following problems?	u Not at all	Several days	More than half the days	Nearly every day
(Use "./"to indicate your answer"				
1. Feeling nervous, anxious or on edge	0	1	2	3
2. Not being able to stop or control worrying	0	1	2	3
3. Worrying too much about different things	0	1	2	3
4. Trouble relaxing	0	1	2	3
5. Being so restless that it is hard to sit still	0	1	2	3
6. Becoming easily annoyed or irritable	0	1	2	3
7. Feeling afraid as if something awful might happen	0	1	2	3

Column totals:

= Total Score

If you checked off any problems, how difficult have these problems made it for you to do your work, take care of things at home, or get along with other people?

Not difficult at all

Somewhat difficult

Very

Difficult

Extremely

Difficult

Table 12. PHQ-9 depression scale

Mood questionnaires will be scored according to Table 13 below.

Table 13. Toxicity grading based on mood questionnaire scores

	PH	Q-9	GAD-7		AD-7
Score	Severity	CTCAE grading	Score	Severity	CTCAE grading
0-4	None	Normal	0-4	None	Normal
5-9	Mild	Grade 1	5-9	Mild	Grade 1
10-19	Moderate	Grade 2	10-14	Moderate	Grade 2
20-27	Severe	Grade 3	≥ 15	Severe	Grade 3

4.1.2.2 Hyperglycemia

In preclinical studies, insulin/glucose homeostasis was impacted in various species (mice, rats, dogs), as expected from the mode of action of buparlisib. In both rats and dogs, at the doses used in the 4-week studies, these effects were minimal. However, in mice treated at high doses (30 or 60 mg/kg/day) a clear induction of insulin resistance/ insensitivity was observed, without clear influence of the dose or the time point of testing.

Histopathologically, pancreas and liver showed changes which are in concordance with this activity.

Grade 4 Hyperglycemia was also observed in an ongoing phase 1a study of buparlisib in patients with solid tumors (CBKM120X2101). Therefore, no patients with uncontrolled diabetes mellitus will be enrolled in this study. In all patients, fasting plasma glucose will obtained at screening and will be monitored throughout the trial. For the treatment of glucose disturbances occurring under buparlisib treatment investigators are advised to adhere to the protocol guidelines outlined in Table 10 and as follows.

4.1.2.2.1 Management of Hyperglycemia

In addition to the dose modification and hyperglycemia treatment guidelines in Tables 9 and 10:

- •• Under the supervision of an endocrinologist, an insulin regimen should be initiated according to institutional standard of care or the Treat-To-Target algorithm for Lantus® (Riddle, Rosenstock, and Gerich 2003).
- ◆◆ For any hyperglycemia ≥ Grade 1, the patient should continue to follow dietary guidelines provided by the American Diabetes Association (American Diabetes Association 2004).
- ◆◆ For each patient, a maximum of 2 dose reductions will be allowed after which the patient should be discontinued from the study. In addition, a patient must discontinue treatment with buparlisib, if after treatment is resumed at a lower dose, hyperglycemia recurs at a worse severity.

- ◆◆ For each patient, once a dose level reduction has occurred, the dose level may not be re-escalated in that patient during future treatment cycles with buparlisib.
- ♦♦ Based upon the results of preliminary clinical data and actual laboratory values (eg, glucose, insulin) generated, the treatment recommendations for study drug-induced hyperglycemia may be modified as needed.

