In case of any occurrence of ALT/ AST/ bilirubin* increase \geq Grade 3 the liver function tests must be monitored weekly or more frequently if clinically indicated until resolved to \leq Grade 1; hereafter the monitoring should be continued every other week or more frequently if clinically indicated until the end of treatment with study medication.

Patients who discontinued study treatment should be monitored weekly, including LFTs* or more frequently if clinically indicated **until resolved to ≤ Grade 1 or stabilization** (no CTCAE grade change over 4 weeks).

Endocrine / Metabolic Fasting Plasma Glucose (FPG) during a cycle of therapy

Maintain dose level, check FPG every week initiate or intensify medication with appropriate anti-diabetic treatment as per investigator's discretion.

Instruct patient to follow dietary guidelines according to local and/or institutional standards for management of diabetes mellitus (such as those provided by the American Diabetes Association during the study.

Consider use of oral anti-hyperglycemic therapy such as metformin blood finger stick every day and if blood glucose levels are worsening for 2 consecutive days FPG assessment is recommended.

Check FPG at least weekly for 8 weeks, then continue checking at least every 2 weeks.

First occurrence:

If signs and symptoms of hyperglycemia (e.g. mental status changes, excessive thirst, polyuria), omit buparlisib immediately and manage as per Grade 3 hyperglycemia.

If asymptomatic, maintain dose and recheck FPG within 24 hours. If grade worsens to grade 3 or 4 follow specific Grade recommendations. If grade improves to grade 1 follow Grade recommendations. If FPG remains at Grade 2, reduce study drug dose to 50% of prior dose and check FPG every week initiate or intensify medication with appropriate anti-diabetic treatment as per investigator's discretion.

Instruct patient to follow dietary guidelines according to local and/or institutional standards for management of diabetes mellitus (such as those provided by the American Diabetes Association during the study.

Consider use of oral anti-hyperglycemic therapy such as metformin blood finger stick every day and if blood glucose levels are worsening for

2 consecutive days FPG assessment is recommended. Check FPG at least weekly for 8 weeks, then continue checking at least every 2 weeks.

Second occurrence:

Discontinue study drug

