Mild mood alteration (or Grade 2 anxiety if present at baseline)	Note : If question 9 (suicidal ideation) on the PHQ-9 has a positive response, or worsens in severity, the patient should be referred for psychiatric consult regardless of the total questionnaire score
Grade 2 Moderate mood alteration (for	Institute appropriate co-medication under the guidance of the psychiatrist. Maintain dose level.
Anxiety only, if worsened from baseline) and if there is no concurrent medical condition that accounts for an acute increase the PHQ score.	If the condition does not resolve to ≤ Grade 1 within 14 days despite medical treatment; then implement 50% dose reduction (continue to co-medicate) Note: If question 9 (suicidal ideation) on the PHQ-9 has a positive response, or worsens in severity, the patient should be referred for psychiatric consult regardless of the total questionnaire score
Grade 3	Discontinue study medication
Severe agitation; hospitalization not indicated	Note : If question 9 on the PHQ-9 has a positive response, or worsens in severity, the patient should be referred for psychiatric consult regardless of the total questionnaire score
Grade 4	Discontinue study medication. Consider hospitalization
Life-threatening consequences; urgent	if appropriate
intervention indicated	Note: If question 9 on the PHQ-9 has a positive response, or worsens in severity, the patient should be referred for psychiatric consult regardless of the total questionnaire score

Table 10. Recommended dose modifications and dose delays for suspected buparlisib treatment-related toxicities	
Worst toxicity	During a cycle of therapy
CTCAE grade* (value)	
Rash	
Grade 1 Macules /papules covering <10% BSA with or without symptoms (e.g. pruritus, burning)	Maintain dose level. Consider to initiate appropriate skin toxicity therapy (such as antihistamines, topical corticosteroids)

Grade 2 Macules/papules covering 10-30% BSA with or without symptoms; limiting instrumental ADLs	Reduce study drug dose to 50% of prior dose. Initiate/intensify appropriate skin toxicity therapy (such as antihistamines, topical corticosteroids)
Grade 3 Macules/papules covering >30% BSA with or without associated symptoms, limiting self-care ADLs	Discontinue study drug According to the investigators discretion, a paired skin biopsy could be obtained (from both an affected and an unaffected skin area for local histopathology assessment) if clinical appropriate

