4.1.1 Monitoring of buparlisib suspected toxicities

Patients whose treatment is interrupted or permanently discontinued due to an adverse event or clinically significant laboratory value, must be followed at least once a week for 4 weeks, and subsequently at 4-week intervals, until resolution or stabilization of the event, whichever comes first. If a patient requires a dose delay of > 21 days from the intended day of the next scheduled dose, then the patient should be discontinued from the study. If the patient requires more than 1 dose reductions, the patient should be discontinued from the study (ie, patients cannot be treated below a 50% dose reduction). All patients must be followed for adverse events and serious adverse events for 28 days following the last dose of buparlisib. All SAEs must be reported to Novartis as detailed in Section 4.3.4.2.

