4.2.2 Sonidegib Administration

The investigator needs to instruct the patient to take the study drug as per protocol. All dosages prescribed and dispensed to the patient and any dose change or interruption must be recorded in the dosage administration record CRF, as appropriately.

Sonidegib Treatment and Treatment Schedule

Study treatments	Pharmaceutical form and route of administration	Dose	Frequency and/or regimen
Sonidegib	Capsule or tablet for oral use	200 QD	daily

Sonidegib will be administered orally with buparlisib, on a continuous once daily dosing schedule at a dose of 200 mg. Participating patients will receive flat doses on mg/ day basis and not according to their body weight or body surface area. Sonidegib is supplied as 200-mg hard gelatin capsules or tablets. Patients will receive 2 capsules or tablets. The shelf-life and storage conditions will be continually assessed based on accelerated and long term stability data Sonidegib. Medication labels will be in the local language (English) and comply with the legal requirements of USA.

Sonidegib should be taken as follows:

- ◆◆ Patients should be instructed to take their once-a day dose at approximately the same time each day
- ◆◆ Each daily dose of Sonidegib should be taken with a glass of water and consumed over as short a time as possible (eg, 1 capsule every 2 minutes)
- ◆◆ Patients should be instructed to swallow capsules whole and to not chew or open them
- •• Each daily dose of Sonidegib should be taken **2 hours after** a light breakfast (eg, consisting of juice, toast and jam). If breakfast was completed at 08:00 a.m., then study drug administration should occur at 10:00 a.m. Food intake should be avoided for at least 1 hour after study drug administration
- ◆◆ Patients must avoid grapefruit, pomegranate, star fruit and Seville (sour) oranges during the entire study. The juices and products containing these fruits may also be avoided
- •• If vomiting occurs during the course of the treatment, then no re-dosing of the patient is allowed before the next scheduled dose

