5.2.1 Buparlisib

Novartis supplies buparlisib as 10-mg and 50-mg hard gelatin capsules. buparlisib will be administered orally once a day, as part of each 28-day cycle. Medication labels comply with the legal requirements of each country and will be printed in the local language. The storage conditions for study drug will be described on the medication label.

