5.2.2 Sonidegib

Sonidegib will be supplied to the study investigators by Novartis. Sonidegib is formulated in capsules and tablets of 200-mg, strengths. The capsules are packaged in HDPE bottles with a child resistant closure. Sonidegib will be administered orally once a day, as part of each 28-day cycle.

Medication labels will conform to local legal requirements. Patient number will be added by the site pharmacist. The storage conditions for study drug will be described on the medication label. Sonidegib will be dispensed at the start of every cycle, as needed. Sonidegib will be administered orally once a day, as part of each 28-day cycle. The investigational site staff will inform each patient of their actual daily dose, and this will be recorded on the appropriate CRF.

When possible, individual doses will consist of the minimum number of capsules equaling the total dose given the available capsule sizes.

Doses for more than 7 days will be placed at 4₀ and patients will be informed of this at drug dispensing.

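### Section 4.1.1 discontinues a patient who needs a second buparlisib dose reduction, but Section 4.1.2.2.1 allows it, taking the dose to 20 mg and below the stated 50% floor.

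*Combined protocol and SAP*

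**What the plan says.** Buparlisib starts at 80 mg once daily (Sections 1.5.2.2.4 and 4.2.1). Two sections limit how often it may be reduced.

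- Section 4.1.1, on monitoring of suspected buparlisib toxicities: "If the patient requires more than 1 dose reductions, the patient should be discontinued from the study". It adds in parentheses that "patients cannot be treated below a 50% dose reduction".
- Section 4.1.2.2.1, on hyperglycemia: for each patient, "a maximum of 2 dose reductions will be allowed", with discontinuation after that. The same list bars re-escalation once the dose has been lowered.

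Table 10 in Section 4.1 sets the size of each cut. For Grade 2 rash it says "Reduce study drug dose to 50% of prior dose". For a first, asymptomatic Grade 2 fasting glucose that is still Grade 2 at recheck, it says "reduce study drug dose to 50% of prior" dose. Grade 2 fatigue is handled the same way. At a second Grade 2 glucose occurrence, Table 10 stops the drug.

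On supply, Section 5.2.1 states: "Novartis supplies buparlisib as 10-mg and 50-mg hard gelatin capsules". For the partner drug, Section 5.2.2 states: "Sonidegib is formulated in capsules and tablets of 200-mg, strengths". Section 4.2.2 adds: "Patients should be instructed to swallow capsules whole and to not chew or open them".

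**The concern.** A patient who meets the criteria for a second buparlisib cut has two opposite dispositions, both written as current protocol text. Section 4.1.1 ends participation. Section 4.1.2.2.1 permits treatment at a dose that Section 4.1.1 says may not be given. Nothing states which section governs.

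What is at stake is patient disposition and safety: whether someone with two drug-related toxicities stops or continues at a quarter of the starting dose, and whether two such patients would be treated alike. With 12 patients per cohort, each disposition is visible in the report.

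A related but separate gap concerns sonidegib. Table 9 repeatedly orders 50% cuts from 200 mg, but only 200 mg units are listed, capsules must be swallowed whole, and tablet splitting is not addressed. The plan does not say how 50% is to be delivered.

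**Working it through.** **Inputs**

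| Input | Value | Source |
|---|---|---|
| Starting dose | 80 mg daily | Sections 1.5.2.2.4, 4.2.1 |
| Size of each cut | 50% of the prior dose | Table 10 (Grade 2 glucose, rash, fatigue) |
| Re-escalation | not allowed | Section 4.1.2.2.1 |
| Cuts allowed, rule A | 1, floor at a 50% reduction | Section 4.1.1 |
| Cuts allowed, rule B | 2 | Section 4.1.2.2.1 |
| Capsules | 10 mg and 50 mg | Section 5.2.1 |

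**Dose after k cuts** = 80 mg × 0.5^k

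- k = 1: 80 × 0.5 = 40 mg, or 50% of the start. This reproduces the floor in Section 4.1.1. Both rules allow it.
- k = 2: 40 × 0.5 = 20 mg. 20/80 = 25% of the start; 20/40 = half the floor. Only rule B allows it.

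Supply does not block the second cut: 40 mg is 4 × 10 mg and 20 mg is 2 × 10 mg.

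**Can a second cut arise?**

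1. From hyperglycemia alone, almost never, because Table 10 stops the drug at a second Grade 2 glucose occurrence.
2. Across toxicities, yes. Grade 2 rash takes 80 mg to 40 mg. A first asymptomatic Grade 2 glucose that persists at recheck then takes 40 mg to 20 mg. Section 4.1.1 discontinues this patient; Section 4.1.2.2.1 lets the patient continue at 20 mg.

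**How often?** The documents cannot answer this. Table 5 (81 patients, single agent) reports all grades and Grade 3-4, not Grade 2 alone and not two toxicities in the same patient. Related Grade 1-2 events, by subtraction:

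- fatigue/asthenia: 31 − 3 = 28; 28/81 = 34.6%
- hyperglycemia: 24 − 4 = 20; 20/81 = 24.7%
- rash: 22 − 4 = 18; 18/81 = 22.2%

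Most patients in that study received 100 mg/day rather than 80 mg. These figures show only that the toxicities for which Table 10 orders a cut at Grade 2 are not rare at Grades 1-2 combined. They are not a rate for the conflict, which needs two qualifying events in one patient.

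**The case against.** The strongest reply is that the rules can be reconciled.

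- **The limit of two is a ceiling, so a site can obey both rules by applying the stricter one.** This would end at 40 mg. The 20 mg dose is indeed not printed anywhere; it is derived. But the protocol does not tell sites to take the stricter rule, and the second section states an allowance, not merely an outer bound.
- **The limit might mean one cut per drug, two in total.** The sentence does not name a drug, the list refers to Tables 9 and 10, and Section 4.1 speaks of reducing either drug or both. This does not fit: the section manages buparlisib hyperglycemia, the next sentence names buparlisib, and Table 9 has no glucose-driven sonidegib cut.
- **Section 4.1 requires dose adjustments to be discussed with the sponsor.** In a single-center study of 24 patients this probably limits the harm. It does not say which limit the discussion should apply.
- **The practical reach is narrow.** This stands. Two different toxicities are needed, and the Table 5 percentages do not measure how often that happens.
- **A strict cap has its own consequences.** This stands in part. Table 14 halves buparlisib for Grade 2 pneumonitis until recovery, which reads as temporary, and a cap of one could discontinue a patient who is benefiting. Section 4.1.1 already accepts that cost, but the revised text should say whether the temporary cut counts.
- **The sonidegib gap is a different issue.** Agreed; it is kept apart and the main conclusion does not depend on it.

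**Conclusion.** The contradiction is real. One current rule allows one buparlisib reduction with a floor of 40 mg; another allows two, which gives 20 mg, or 25% of the starting dose. The 20 mg figure assumes that both cuts are halvings of the prior dose, as Table 10 words them for glucose, rash and fatigue, and that the dose is not re-escalated between them. The conflict applies essentially to patients with two different qualifying toxicities, and their number cannot be fixed from the documents. Sample size, error rate and power are unaffected, and no shift in the response rate is claimed. It should be corrected because it leaves a dosing and discontinuation rule undefined for patients who are already having toxicity.

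**What to change.** In Section 4.1.2.2.1, replace the allowance of two reductions with one buparlisib reduction per patient, counted across all toxicities, and state that a patient who needs a second is discontinued. This matches the 40 mg floor already in Section 4.1.1. In the same sentence, say whether the temporary pneumonitis cut in Table 14 counts toward the one.

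Separately, because the cap does not solve it, add a sentence on how a 50% sonidegib reduction from 200 mg is to be given. One possibility, for the sponsor to confirm, is 200 mg on alternate days.

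The cost is one changed number with a short clarification, and one added sentence. No new data or visits are needed.

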4.1.2.3 Cardiac events

Cardiac safety studies, conducted in vitro and in vivo, did not indicate a prominent electrophysiological risk. The only effect considered relevant was a trend towards an increase in systolic and diastolic blood pressure, observed in two dog telemetry studies. As a precaution in the first-in man study with buparlisib no patients with a severe or unstable cardiac disease or cardiac disease requiring continuous treatment, and no patients with uncontrolled hypertension will be enrolled in early clinical studies. In addition, all patients will be assessed for cardiac diseases before start of treatment, while all patients enrolled in the trial will undergo regular cardiac monitoring throughout the conduct of the trial. For the treatment of acute cardiac events occurring under buparlisib treatment investigators are advised to adhere to the protocol guidelines. Vital signs, including pulse rate and blood pressure, will closely be followed during the early clinical studies.

4.1.2.3.1 Management of Cardiac events

At the screening visit a 12-lead electrocardiogram (ECG), will be performed to assess eligibility.

4.1.2.3.2 Guidelines for the treatment of study drug induced stomatitis/ oral mucositis

General guidance and management include patient awareness and early intervention. Evaluation for herpes virus or fungal infection should be considered.

Patients should be informed about the possibility of developing mouth ulcers/ oral mucositis and instructed to report promptly any signs or symptoms to their physician, Patients should be educated about good oral hygiene, instructed to avoid spicy/acidic/salty foods, and should follow the following guidelines:

- ◆◆ For mild toxicity (Grade 1), use conservative measures such as non-alcoholic mouth wash or salt water (0.9%) mouth wash several times a day until resolution.
- For more severe toxicity (Grade 2 in which case patients have pain but are able to maintain adequate oral alimentation, or Grade 3 in which case patients cannot maintain adequate oral alimentation), the suggested treatments are topical analgesic mouth treatments (ie, local anesthetics such as benzocaine, butyl aminobenzoate, tetracaine hydrochloride, menthol, or phenol) with or without topical corticosteroids, such as triamcinolone oral paste 0.1% (Kenalog in Orabase[®]), or as per local practice.
- ◆◆ Agents containing alcohol, hydrogen peroxide, iodine, and thyme derivatives may tend to worsen mouth ulcers. It is preferable to avoid these agents.

Antifungal agents should be avoided unless a fungal infection is diagnosed as they may interfere with buparlisib metabolism. Oral or systemic liver enzyme inhibitors such as topical antifungal creams are allowed.

